9. STUDY CALENDAR

9.1. Cohorts A and B

Study Procedures	Pre- screen	Screen	Cycle (28 days) ²¹ EOT ²²		Safety FU ²³	Clinical FU ²⁴	Survival FU ²⁵
Visit Windows (days) ¹	N/A	-28 to D1	± 3 ± 7		+14	± 14	± 14
Nivolumab/ Relatlimab			X				
Informed Consent		X					
Inclusion/Exclusion Criteria		X					
Demographics		X					
Medical, Cancer, & Con Med History ²		X					
Mucin/PD-L1 CPM	X						
Con Meds, Adverse Events ³			X	X	X	X	
Physical Exam, ECOG PS ³		X	X	X		X	
Vitals ⁴		X	X	X		X	
Height ⁵		X					
Weight		X	X	X		X	
Oxygen Saturation		X	X	X			
Virology ⁶		X					
Hematology, Chemistry ^{7, 12}		X	X	X		X	
Endocrine ^{8, 12}		X	X	X			
Cardiac Troponin ^{9, 12}		X	X				
Urinalysis ^{10, 12}		X					
Pregnancy Test ^{11, 12}		X	X				
CEA ¹²		X	X	X		X	
ECG ¹³		X					
Echocardiogram ¹⁴		X					
CT/MRI, RECIST/iRECIST ¹⁵		X	X	X		X	
Whole Blood (up to 10cc) 16,26			X				
PBMC ^{17, 18, 26}			X (see footnote for schedule)				
Plasma (up to 20cc) ^{17, 26}			X (see footnote for schedule)				
Serum (up to 5cc) ^{17, 26}			X (see footnote for s				
Stool and Oral Wash Samples ^{19, 26}			X (see footnote for s				
Microbiome Questionnaire ¹⁹			X (see footnote for schedule)				
Tumor Biopsies ^{20, 26}		X	X				
Archival Tissue ²⁶	X						
Survival Follow-up							X

In order to minimize the need for research-only in-person visits, telemedicine visits may be substituted for in person clinical trial visits or portions of clinical trial visits where determined to be appropriate and where determined by the investigator not to increase the participants risks. Prior to initiating telemedicine for study visits the study team will explain to the participant, what a telemedicine visit entails and confirm that the study participant is in agreement and able to proceed with this method. Telemedicine acknowledgement will be obtained in accordance with the Guidance for Use of Telemedicine in Research. In the event telemedicine is not deemed feasible, the study visit will proceed as an in-person visit. Telemedicine visits will be conducted using HIPAA compliant method approved by the Health System and within licensing restrictions.

- 1: If necessary, a scheduled cycle may be delayed for up to 1 week. Longer delays to be approved by the IND Sponsor.
- 2: Cancer history includes: primary site of cancer, gross location of primary tumor, secondary sites of cancer, histology, histologic grade, date of initial diagnosis, date of metastatic diagnosis, prior cancer therapy regimens, MSI testing, and tumor mutation testing.
- 3: Complete physical examination and assessment of ECOG PS will be completed at baseline; focused physical examinations and assessment of ECOG PS will be conducted thereafter. Exams, concomitant medication, AE assessments, and ECOG PS can be evaluated up to 3 days prior to infusion.
- 4: Blood pressure, pulse, and temperature. Vitals will be collected prior to and at the end of the nivolumab/relatlimab infusion (+ 15 minutes).
- 5: Height will be obtained at or prior to baseline only.
- 6: Virology screen: HIV antibody, hepatitis B surface antigen and hepatitis C antibody; additional virology may also be evaluated. Subjects who are hepatitis C antibody positive and confirmed negative viral load at screening will be allowed to enroll.
- 7: Clinical hematology: CBC with differential ANC, ALC, AEC, and platelet count; serum chemistry: sodium, potassium, chloride, bicarbonate, glucose, BUN, creatinine, ALT, AST, alkaline phosphatase, total bilirubin, direct bilirubin, amylase, lipase, total protein, albumin, calcium, magnesium, and phosphorus. LDH at baseline only.
- 8: TSH (Total T3 and free T4 if TSH abnormal and clinically indicated).
- 9: T (cTnt) or I (cTnI). To be obtained on C1D1, C2D1, and C3D1 only. Troponin elevations will require the participant to undergo a cardiac evaluation per **Section 5.2**. Following this evaluation, determination of further treatment will be based on the discussion with the IND Sponsor.
- 10: Bilirubin, blood, glucose, ketones, leukocytes, nitrite, pH, color, protein, RBC and WBC count, and specific gravity.
- 11: Pregnancy tests will be administered to WOCBP: serum pregnancy test is required at screening; serum or urine pregnancy tests are required before doses on Day 1 of dosing weeks.
- 12: Labs may be collected within a window of up to 3 days prior to dosing.
- 13: ECG should be performed at baseline (within 14 days prior to first dose on C1D1), if clinically indicated, or at elevation of troponin levels per **Section 5.2**.
- 14: LVEF assessment with documented LVEF \geq 50% by either TTE or MUGA (TTE preferred test) within 6 months from first study drug administration.
- 15: Spiral CT of thorax, abdomen and pelvis (and other imaging studies as clinically indicated to evaluate suspected sites of metastatic disease). If a subject cannot have a CT scan (e.g., allergy to contrast dye), an MRI should be performed. On study radiologic evaluations and tumor measurements (RECIST/iRECIST per **Appendix C and D**) will be at baseline, 12 weeks (+/- 2 week), every 8 weeks (+/- 2 week) through week 52, and then every 12 weeks (+/- 2 week) thereafter including the EOT evaluation (± 4 weeks). The EOT scans do not need to be repeated if

- one has been done within the past 6 weeks. Weeks are in reference to calendar week and should not be adjusted due to dosing delays.
- 16: Baseline only (any time prior to the first dose after eligibility is met)
- 17: Whole blood for PBMC, plasma, and serum will be collected at baseline (any time prior to the first dose after eligibility is met), 4 weeks (+/- 1 week), every 16 weeks (+/- 2 week) through week 52, and then every 24 weeks (+/- 2 week) thereafter including the EOT evaluation. Weeks are in reference to calendar week and should not be adjusted due to dosing delays.
- 18: Up to 120cc of whole blood for PBMC isolation will be collected at baseline (any time prior to the first dose after eligibility is met) and at week 4. Up to 150 cc will be collected at subsequent time points.
- 19: Stool, oral wash (and/or buccal mucosal) specimens, and microbiome questionnaire will be obtained when available. All stool specimens should be collected within 72 hours (and ideally within 24 hours) of the patient's appointment. Baseline specimens may be obtained any time prior to the first dose after eligibility is met. On study stool specimens will be obtained every 12 weeks (+/- 2 week) through week 52, and then annually thereafter including the EOT evaluation (± 4 weeks). Oral wash and/or buccal swab will be collected at baseline, once during treatment and annually thereafter including the EOT evaluation (± 4 weeks). Additional samples may be obtained if the patient has any drug-related toxicity at any point during the trial. Detailed instructions for stool and oral wash collection and shipment are provided in the Laboratory Manual.
- 20: Tumor biopsies to be taken (if a subject's tumor is thought to be reasonably safe and easy to biopsy) at baseline (any time prior to the first dose after eligibility is met) and at Cycle 2 (4-6 cores per time point). The Cycle 2 biopsy has a ± 1 week window. Additional optional biopsies may be obtained later in the course of study treatment. Fine needle aspiration will not be acceptable. Detailed instructions for tissue collection, processing and shipment are provided in the Laboratory Manual.
- 21: Cycle 1 Day 1 evaluations do not need to be repeated if they were conducted within 3 days of the pre-study evaluations. Window of +7 days is for cycle 2 and beyond.
- 22: EOT visit will occur 30 (±7) days after the final dose (or within 7 days prior to initiation of a new anti-cancer treatment, whichever comes first). NOTE: CT scan assessment at EOT will occur 30 days (± 4 weeks) after the final dose. If the EOT visit occurs early, an assessment for AEs should be made by telephone or email on day 30 (±1) after last study dose.
- 23: Subjects who discontinue treatment should be contacted by telephone or email at 100 days (+ 14 day reporting window) from their last dose of study drug or within 7 days before initiation of a new antineoplastic treatment (whichever comes first) to assess for treatment related toxicities. In addition, all SAEs occurring during this time should be reported as well.
- 24: Subjects who discontinue treatment without disease progression (Section 4.12.2) will enter the clinical follow-up portion of the trial. Clinical follow-up visits will occur every 12 weeks (± 2 weeks) until progression. After disease progression, subjects will enter the survival follow-up portion of the trial.
- 25: Subjects who discontinue treatment and have disease progression (Section 4.12.3) will enter the survival follow-up portion of the trial. Subjects should be contacted every 12 weeks (± 2 weeks) to monitor overall survival. Information of other cancer therapies after discontinuation from the study treatment will be collected as well.
- 26: Research samples will be collected at the discretion of the PI based on availability of supplies and safety of patient and staff.

9.2. Cohort C

Study Procedures	Screen	Cycle (28 days) ²¹	EOT ²²	Safety FU ²³	Clinical FU ²⁴	Survival FU ²⁵
Visit Windows (days) ¹	-28 to D1	± 3	± 7	+14	± 14	± 14
Nivolumab/ Relatlimab		X^{27}				
Informed Consent	X					
Inclusion/Exclusion Criteria	X					
Demographics	X					
Medical, Cancer, & Con Med History ²	X					
Con Meds, Adverse Events ³		X	X	X	X	
Physical Exam, ECOG PS ³	X	X	X		X	
Vitals ⁴	X	X	X		X	
Height ⁵	X					
Weight	X	X	X		X	
Oxygen Saturation	X	X	X			
Virology ⁶	X					
Hematology, Chemistry ^{7, 12}	X	X	X		X	
Endocrine ^{8, 12}	X	X	X			
Cardiac Troponin, CPK ^{9, 12}	X	X				
Urinalysis ^{10, 12}	X					
Pregnancy Test ^{11, 12}	X	X				
CEA ¹²	X	X	X		X	
ECG ¹³	X					
Echocardiogram ¹⁴	X					
CT/MRI, RECIST/iRECIST ¹⁵	X	X	X		X	
Whole Blood (up to 10cc) 16,26		X				
PBMC ^{17, 18, 26}		X (see footnote for schedule)				
Plasma (up to 20cc) ^{17, 26}		X (see footnote for schedule)				
Serum (up to 5cc) ^{17, 26}		X (see footnote for schedule)				
Stool and Oral Wash Samples ^{19, 26}		X (see footnote for schedule)				
Microbiome Questionnaire ¹⁹		X (see footnote for schedule)				
Tumor Biopsies ^{20, 26}	X	X				
Archival Tissue ²⁶		X				
Survival Follow-up						X

In order to minimize the need for research-only in-person visits, telemedicine visits may be substituted for in person clinical trial visits or portions of clinical trial visits where determined to be appropriate and where determined by the investigator not to increase the participants risks. Prior to initiating telemedicine for study visits the study team will explain to the participant, what a telemedicine visit entails and confirm that the study participant is in agreement and able to proceed with this method. Telemedicine acknowledgement will be obtained in accordance with the Guidance for Use of Telemedicine in Research. In the event telemedicine is not deemed feasible, the study visit will proceed as an in-person visit. Telemedicine visits will be conducted using HIPAA compliant method approved by the Health System and within licensing restrictions.

- 1: If necessary, a scheduled cycle may be delayed for up to 1 week. Longer delays to be approved by the IND Sponsor.
- 2: Cancer history includes: primary site of cancer, gross location of primary tumor, secondary sites of cancer, histology, histologic grade, date of initial diagnosis, date of metastatic diagnosis, prior cancer therapy regimens, MSI testing, and tumor mutation testing.
- 3: Complete physical examination and assessment of ECOG PS will be completed at baseline; focused physical examinations and assessment of ECOG PS will be conducted thereafter. Exams, concomitant medication, AE assessments, and ECOG PS can be evaluated up to 3 days prior to infusion. Additional weekly visits with AE assessment will occur through Week 8 (C3D1) for patients that received the 480mg or 960mg dose of relatlimab.
- 4: Blood pressure, pulse, and temperature. Vitals will be collected prior to and at the end of the nivolumab/relatlimab infusion (+ 15 minutes).
- 5: Height will be obtained at or prior to baseline only.
- 6: Virology screen: HIV antibody, hepatitis B surface antigen and hepatitis C antibody; additional virology may also be evaluated. Subjects who are hepatitis C antibody positive and confirmed negative viral load at screening will be allowed to enroll.
- 7: Clinical hematology: CBC with differential ANC, ALC, AEC, and platelet count; serum chemistry: sodium, potassium, chloride, bicarbonate, glucose, BUN, creatinine, ALT, AST, alkaline phosphatase, total bilirubin, direct bilirubin, amylase, lipase, total protein, albumin, calcium, magnesium, and phosphorus. LDH at baseline only.
- 8: TSH (Total T3 and free T4 if TSH abnormal and clinically indicated).
- 9: T (cTnt) or I (cTnI). To be obtained on C1D1, C2D1, and C3D1 only. For patients receiving 480mg or 960mg dose of Relatlimab, cTnt or cTnI AND CPK will also be obtained weekly (± 3 day window) through and including C3D1. Troponin elevations will require the participant to undergo a cardiac evaluation per **Section 5.2**. Following this evaluation, determination of further treatment will be based on the discussion with the IND Sponsor.
- 10: Bilirubin, blood, glucose, ketones, leukocytes, nitrite, pH, color, protein, RBC and WBC count, and specific gravity.
- 11: Pregnancy tests will be administered to WOCBP: serum pregnancy test is required at screening; serum or urine pregnancy tests are required before doses on Day 1 of dosing weeks.
- 12: Labs may be collected within a window of up to 3 days prior to dosing.
- 13: ECG should be performed at baseline (within 14 days prior to first dose on C1D1), if clinically indicated, or at elevation of troponin levels per **Section 5.2**.
- 14: LVEF assessment with documented LVEF \geq 50% by either TTE or MUGA (TTE preferred test) within 6 months from first study drug administration.
- 15: Spiral CT of thorax, abdomen and pelvis (and other imaging studies as clinically indicated to evaluate suspected sites of metastatic disease). If a subject cannot have a CT scan (e.g., allergy to contrast dye), an MRI should be performed. On study radiologic evaluations and tumor measurements (RECIST/iRECIST per **Appendix C and D**) will be at baseline, 12 weeks (+/- 2 week), every 8 weeks (+/- 2 week) through week 52, and then every 12 weeks (+/- 2 week) thereafter including the EOT

- evaluation (\pm 4 weeks). The EOT scans do not need to be repeated if one has been done within the past 6 weeks. Weeks are in reference to calendar week and should not be adjusted due to dosing delays.
- 16: Baseline only (any time prior to the first dose after eligibility is met)
- 17: Whole blood for PBMC, plasma, and serum will be collected at baseline (any time prior to the first dose after eligibility is met), 4 weeks (+/- 1 week), every 16 weeks (+/- 2 week) through week 52, and then every 24 weeks (+/- 2 week) thereafter including the EOT evaluation. Weeks are in reference to calendar week and should not be adjusted due to dosing delays.
- 18: Up to 120cc of whole blood for PBMC isolation will be collected at baseline (any time prior to the first dose after eligibility is met) and at weeks 2 and 4. Up to 150 cc will be collected at subsequent time points.
- 19: Stool, oral wash (and/or buccal mucosal) specimens, and microbiome questionnaire will be obtained when available. All stool specimens should be collected within 72 hours (and ideally within 24 hours) of the patient's appointment. Baseline specimens may be obtained any time prior to the first dose after eligibility is met. On study stool specimens will be obtained every 12 weeks (+/- 2 week) through week 52, and then annually thereafter including the EOT evaluation (± 4 weeks). Oral wash and/or buccal swab will be collected at baseline, once during treatment and annually thereafter including the EOT evaluation (± 4 weeks). Additional samples may be obtained if the patient has any drug-related toxicity at any point during the trial. Detailed instructions for stool and oral wash collection and shipment are provided in the Laboratory Manual.
- 20: Tumor biopsies to be taken (if a subject's tumor is thought to be reasonably safe and easy to biopsy) at baseline (any time prior to the first dose after eligibility is met) and at Cycle 2 (4-6 cores per time point). The Cycle 2 biopsy has a ± 1 week window. Additional optional biopsies may be obtained later in the course of study treatment. Fine needle aspiration will not be acceptable. Detailed instructions for tissue collection, processing and shipment are provided in the Laboratory Manual.
- 21: Cycle 1 Day 1 evaluations do not need to be repeated if they were conducted within 3 days of the prestudy evaluations. Window of +7 days is for cycle 2 and beyond.
- 22: EOT visit will occur 30 (±7) days after the final dose (or within 7 days prior to initiation of a new anticancer treatment, whichever comes first). NOTE: CT scan assessment at EOT will occur 30 days (± 4 weeks) after the final dose. If the EOT visit occurs early, an assessment for AEs should be made by telephone or email on day 30 (±1) after last study dose.
- 23: Subjects who discontinue treatment should be contacted by telephone or email at 100 days (+ 14 day reporting window) from their last dose of study drug or within 7 days before initiation of a new antineoplastic treatment (whichever comes first) to assess for treatment related toxicities. In addition, all SAEs occurring during this time should be reported as well.
- 24: Subjects who discontinue treatment without disease progression (**Section 4.12.2**) will enter the clinical follow-up portion of the trial. Clinical follow-up visits will occur every 12 weeks (± 2 weeks) until progression. After disease progression, subjects will enter the survival follow-up portion of the trial.
- 25: Subjects who discontinue treatment and have disease progression (Section 4.12.3) will enter the survival follow-up portion of the trial. Subjects should be contacted every 12 weeks (± 2 weeks) to monitor overall survival. Information of other cancer therapies after discontinuation from the study treatment will be collected as well.
- 26: Research samples will be collected at the discretion of the PI based on availability of supplies and safety of patient and staff.
- 27: If nivolumab and relatlimab are being administered sequentially (due to Relatlimab 480 or 960mg dose), the order of administration is nivolumab followed by relatlimab. Subjects should be observed for a minimum of 30 minutes between each infusion.

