5.2. Dose Delays

In some cases, the natural history of select AEs associated with immunotherapy can differ from and be more severe than AEs caused by other therapeutic classes. Early recognition and management may mitigate severe toxicity.

Guidance for Investigators is provided in the current relatlimab and nivolumab Investigator's Brochures. Additionally, management algorithms have been developed to assist Investigators with select toxicities and can be found in **Appendix B.** Toxicities for which management algorithms have been developed include:

- Pulmonary
- Gastrointestinal
- Hepatic
- Endocrine
- Dermatologic
- Neurologic
- Renal
- Myocarditis

Subjects who experience the following must have all study drugs held:

- Select drug-related AEs and drug-related laboratory abnormalities:
 - o Grade ≥ 1 pneumonitis
 - o Increase from baseline of ≥ one grade (to at least grade 2) of AST, ALT, and/or total bilirubin
 - \circ Grade ≥ 2 creatinine
 - \circ Grade \geq diarrhea or colitis
 - o Grade \geq 2 neurological AE
 - o Grade 4 amylase and/or lipase abnormalities regardless of symptoms or clinical manifestations
 - o Troponin >ULN requires a dose delay to allow for prompt cardiac evaluation
 - Between > 1 to $2 \times ULN$ will be permitted if a repeat assessment remains $\leq 2 \times ULN$ and patient undergoes a cardiac evaluation
- Any AE, laboratory abnormality, or intercurrent illness which, in the judgment of the investigator, warrants delaying the dose of study drug.

Subjects not meeting guidelines for permanent discontinuation will be permitted to resume therapy when the treatment-related AE(s) resolve to grade ≤ 1 or baseline value, with the following exceptions:

- If the toxicity resolves to ≤ Grade 1 or baseline > 6 weeks after last dose, but the subject does not otherwise meet criteria for permanent discontinuation, and the Investigator believes that the subject is deriving clinical benefit, then the subject may be eligible to resume the study drugs following the approval of the IND Sponsor.
- Subjects with grade 4 drug-related amylase and/or lipase increase that is not associated with symptoms or clinical manifestations of pancreatitis can be restarted on therapy once the levels have recovered to grade 3 or less.
- Subjects may resume treatment in the presence of Grade 2 fatigue.

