6.1.1 Adverse Event

An AE is defined as any undesirable sign, symptom or medical condition occurring after starting the study drug (or therapy) even if the event is not considered to be related to the study. An undesirable medical condition can be symptoms (e.g., nausea, chest pain), signs (e.g., tachycardia, enlarged liver) or the abnormal results of an investigation (e.g., laboratory findings, electrocardiogram). Medical conditions/diseases present before starting the study treatment are only considered AEs if they worsen after starting the study treatment (any procedures specified in the protocol). New medical conditions / diseases occurring before starting the study treatment but after signing the informed consent form will not be recorded as AEs. Additionally, expected progression of the disease being studied will not be recorded as an adverse event.

Laboratory abnormalities: Laboratory abnormalities present at the screening visit will be recorded as pre-treatment signs and symptoms. After study treatment administration, all grade 3 and 4 clinical laboratory results that represent an increase in severity from baseline will be reported as AEs. A grade 1 or 2 clinical laboratory abnormality should be reported as an AE only if it is considered clinically significant by the investigator (induce clinical signs or symptoms or require corrective therapy), meets the definition of an SAE, or requires the participant to have study drug discontinued or interrupted. It is expected that

wherever possible, the clinical rather than laboratory term would be used by the reporting investigator (e.g., anemia versus low hemoglobin value).

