12.2. Safety Analysis

The safety analysis will be performed in all treated subjects. AE data will be listed individually and incidence of AEs summarized by system organ class and preferred terms within a system organ class for each cohort. When calculating the incidence of AEs, each AE (based on preferred terminology defined by CTCAE version 5.0) will be counted only once for a given subject. In analyses of grade and causality, if the same AE occurs on multiple occasions, the highest grade and strongest relationship to study drug will be assumed. If 2 or more AEs are reported as a unit, the individual terms will be reported as separate experiences.

Changes in vital signs, hematology and clinical chemistry parameters from baseline to the end of the study will be examined. Toxicity will be tabulated by type and grade. Toxicities will be characterized according to the CTCAE version 5.0. Treatment-emergent changes from normal to abnormal values in key laboratory parameters will be identified.

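### Cohort C on relatlimab 480/960 mg is watched more closely to week 8 than Cohorts A/B, and the per-cohort safety tables in 12.2 cannot separate this from dose

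*Combined protocol and SAP*

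**What the plan says.** **Cohort C, 480 or 960 mg (Section 9.2).** Footnote 9 adds to the day-1 draws: "cTnt or cTnI AND CPK will also be obtained weekly (± 3 day window) through and including C3D1". Footnote 3 adds visits: "Additional weekly visits with AE assessment will occur through Week 8 (C3D1) for patients that received the 480mg or 960mg dose of relatlimab". The calendar row reads "Cardiac Troponin, CPK".

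**Cohorts A/B, 160 mg (Section 9.1).** The row reads "Cardiac Troponin", and footnote 9 limits the draws: "To be obtained on C1D1, C2D1, and C3D1 only". CPK is absent from the chemistry panel in footnote 7, and there are no added weekly visits. Both calendars also mark a screening troponin.

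**Reason for the difference.** Section 1.4 presents the closer monitoring as a deliberate safety measure for the higher doses.

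**How a laboratory value becomes a reported event.** Under 6.1.1, every grade 3-4 laboratory result that has worsened from baseline is an AE, with no symptom requirement. A grade 1-2 result is an AE if the investigator judges it clinically significant, if it meets the SAE definition, or if it "requires the participant to have study drug discontinued or interrupted". Section 5.2 adds: "Troponin >ULN requires a dose delay to allow for prompt cardiac evaluation".

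**Analysis.** Section 12.2 plans "incidence of AEs summarized by system organ class and preferred terms within a system organ class for each cohort". Section 10.2 lists cardiac troponin and the number of patients with grade 3 or higher drug-related toxicities among the safety measures. Section 12.2 does not mention the unequal schedules and plans no between-cohort toxicity test.

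**The concern.** A laboratory abnormality that causes no symptoms is recorded only if someone draws the blood. With more draws, more short-lived elevations are seen, whatever their true frequency. CPK is the extreme case: scheduled testing can find an elevation only in Cohort C.

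Safety is the trial's only secondary objective, and the per-cohort tables are its safety description of the 160 mg and the 480/960 mg regimens. Those columns will stand next to each other. An excess of troponin or CPK findings in Cohort C could come from the dose, from the extra draws or from both, and nothing in 12.2 helps a reader tell which. The grade 3 or higher measure is exposed too: a drug-related grade 3 CPK rise counts there without symptoms, and scheduled testing looks for it in one cohort only.

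**Working it through.** **Plan's own figure.** The documents give no rate, sample size or power for toxicity, so there is no stated figure to reproduce on this point. The response-rate design (18 + 14 = 32, at least 4 responses) does reproduce, with exact power 0.9015 at 20% and type I error 0.0721 at 5%, but it has no bearing here.

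**Step 1: scheduled time points, weeks 0 to 8** (footnotes 3 and 9 of Sections 9.1 and 9.2; 28-day cycles; no dose delay; Cohort C patient on 480/960 mg throughout)

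| | Cohorts A/B | Cohort C |
|---|---|---|
| Troponin, including C1D1 | 3 (weeks 0, 4, 8) | 9 (weeks 0 to 8) |
| Troponin after first dose | 2 | 8 |
| Troponin strictly between C1D1 and C2D1 | 0 | 3 |
| CPK | 0 | weekly |
| AE visits, including C1D1 | 3 | 9 |

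**Step 2: share of elevations that a scheduled draw would meet.** Assumptions, none of them in the documents: one elevation per affected patient, lasting D days, with onset uniform over days 0 to 56. It is found if a draw falls while it lasts. With draws every g days, the share found is min(1, D/g), where g = 28 for A/B and g = 7 for Cohort C.

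| Duration D | A/B: D/28 | Cohort C: D/7 |
|---|---|---|
| 3 days | 3/28 = 11% | 3/7 = 43% |
| 7 days | 7/28 = 25% | 100% |
| 14 days | 14/28 = 50% | 100% |
| 21 days | 21/28 = 75% | 100% |
| 28 days or more | 100% | 100% |

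**Step 3: observed rate at equal true risk.** Observed rate = true 8-week rate q × share found. Patients are out of 32, the maximum per cohort.

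| q (assumed) | D | A/B | Cohort C | Patients of 32 |
|---|---|---|---|---|
| 5% | 7 days | 1.25% | 5% | 0.4 vs 1.6 |
| 10% | 7 days | 2.5% | 10% | 0.8 vs 3.2 |
| 10% | 14 days | 5% | 10% | 1.6 vs 3.2 |
| 20% | 7 days | 5% | 20% | 1.6 vs 6.4 |
| any | 28 days or more | q | q | equal |

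These are rates of detected troponin elevations, not AE rates. For CPK no ratio can be formed, because A/B have no scheduled test.

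**The case against.** **No planned analysis is wrong.** The objective is to characterise the toxicity of the combination, 12.2 plans no between-cohort contrast, and the closer monitoring is open and intentional. This stands. The point limits interpretation; it is not an error in a test.

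**The dose-delay route to an AE is weak for transient rises.** Doses fall every 28 days. A grade 1-2 troponin rise at week 1 to 3 that clears before the next dose need not delay anything, while one that persists to C2D1 or C3D1 meets a draw in A/B as well. Section 5.2 has no CPK-specific hold. This largely stands for grade 1-2 values. It does not reach worsened grade 3-4 values, which are AEs under 6.1.1 regardless, nor an evaluation that overruns the dose date, nor troponin results summarised as a safety measure under 10.2.

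**Existing rules limit the exposure.** Non-serious AEs are collected continuously in all cohorts (6.5.1), 12.2 counts each AE once per subject, and asymptomatic laboratory abnormalities are excluded from unacceptable toxicity (4.7). So the effect falls mainly on transient or asymptomatic findings. The 4.7 exclusion does not extend to the grade 3 or higher measure in 10.2.

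**Stronger readings that the documents do not support.** A reader might infer that any excess in Cohort C is due to surveillance alone. It cannot be, on these documents: relatlimab dose also differs (160 versus 480 or 960 mg), so neither factor can be named the sole cause. A reader might also treat each draw as an independent chance of an elevation and obtain large contrasts from 2 versus 8 draws. The documents give no per-draw rate, serial values in one patient are unlikely to be independent, and the result would be a chance of any value above ULN, not an AE incidence. Finally, the absence of scheduled troponin after C3D1 applies to every cohort and says nothing about unequal detection.

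**Conclusion.** The point holds as a limit on interpretation. Scheduled surveillance to week 8 differs by cohort, it moves with dose, and the per-cohort tables in 12.2 cannot separate the two. Detected troponin and CPK abnormalities, and AEs arising from them, can be more frequent in Cohort C at equal true risk.

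The size cannot be fixed from the documents. Under the assumptions above, with a 10% true rate, the surplus found in Cohort C is about 2.4 patients of 32 (3.2 - 0.8) for 7-day elevations, 1.6 (3.2 - 1.6) for 14-day elevations, and none at 28 days or more. The draw counts assume that the patient stays on 480/960 mg to C3D1.

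Which Cohort C patients fall under the weekly schedule is also not fully settled. Footnote 3 of Section 9.2 covers those who have had 480 or 960 mg, while footnote 9 covers those currently on it. A patient reduced to 160 mg before C3D1 is therefore treated differently by the two footnotes.

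**What to change.** Keep the full all-treated AE tables by cohort unchanged, and add to Section 12.2:

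1. A statement that scheduled ascertainment of troponin, CPK and AEs differs between Cohort C on 480/960 mg and Cohorts A/B to week 8.
2. A supplementary by-cohort table of troponin abnormalities that uses only the draws common to all cohorts: C1D1, C2D1 and C3D1.
3. CPK results presented for Cohort C only, outside any cross-cohort reading.

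Reconcile footnotes 3 and 9 of Section 9.2 for Cohort C patients reduced to 160 mg, so that it is clear whose schedule includes the weekly draws and visits.

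Events found at the extra Cohort C visits should not be moved out of the main by-cohort tables. That could hide genuine higher-dose toxicity, and it would require each AE to be attributed to the visit that found it.

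The cost is some wording and one extra table, built from dated laboratory results that the trial already collects. Clinical monitoring does not change. The downside is that the new table omits Cohort C's interim draws, so it must sit beside the full table and not replace it.
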